## 7.0 Study Description

### 7.1 \* Lay Summary

Please provide a summary of your study in lay language. The summary should be no more than a half page (500 words or less) and should contain a clear statement of the rationale for the study.

The development of industrialization with increased food consumption and sedentary has given rise to an obesity pandemic, which affects up to 30% of the population in countries like US, these populations being at greater risk for cardiovascular diseases, and diabetes. More than obesity per se, visceral obesity is associated with metabolic diseases (1) that cluster together and clinically defined metabolic syndrome (MetS). MetS comprises individuals with at least three of the 5 of the following factors: abdominal obesity, high blood triglycerides, low HDL ("good cholesterol"), high blood pressure and elevated fasting glucose (2). Metabolic syndrome is associated with a low-grade inflammation or metaflammation characterized by an infiltration of immune cells particularly in the adipose tissue, the liver and the pancreas (3) that is thought to be responsible for the induction of insulin resistance. It is thought that obesity predisposes to other diseases such as cancer, asthma but only little attention has been given to infectious diseases (4, 5). Studies have shown that obesity increases the risk of severe influenza infection (6) and associated death and reduces the efficacy of influenza vaccine in the obese population (7) but yet, the molecular mechanisms have not been described. Immune dysfunctions associated with obesity are suspected to play a major role but obesity is often associated with respiratory disorders that could directly explain the increased susceptibility to influenza infection (8). Also, metabolically healthy obesity is less associated with metaflammation (9). Therefore, we would like to focus particularly on metabolic syndrome, and determine how it influences immune response to viruses. We are thus hypothesizing that differences in the innate immune responses between individual with or without metabolic syndrome impact viral infection and vaccine outcome. Recent studies involving complex biological analysis and computational modeling have shown that the ability of an individual to positively respond to influenza vaccine can be molecularly predicted by looking at markers in the blood cells (10-12). We will perform seasonal influenza vaccination in people with or without metabolic syndrome to determine if the late adaptive response assessed by antibodies titers is different between the two groups and correlates with the early immune response assessed by gene expression profile in whole blood cells. Healthy nutritional habits along with increased physical activities should be best at preventing the development of metabolic syndrome but socio-economical issues are slowing the implementation of these changes. Therefore, as metabolic syndrome is raising public health concerns, it is important to understand why the metabolic syndrome affects susceptibility to diseases. The project we propose will contribute to a better understanding of the inflammatory phenotype associated with metabolic syndrome and establish for the first time if it affects the immune protection against infectious diseases and particularly against influenza virus infection. Our results are important to determine if the population affected by metabolic syndrome should receive anti-influenza treatment in priority in the context of a severe influenza epidemic.

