**11.0 Objectives and Rationale****11.1 \* Overview**

Briefly state the *purpose of this study*. Give enough background and rationale to provide both scientists and lay members of the IRB and ACCTS with the basis for exposing human subjects to the risks involved.

Metabolic syndrome is associated with a chronic inflammatory state that is thought to be determinant in the development of diabetes and cardiovascular events. Excess energy intake results in a hypertrophy of the adipose tissue that generates the production of pro-inflammatory molecules like TNF alpha, and IL-6, which turn on the immune response. This results in infiltration of immune cells like macrophages and natural-killer (NK) cells in the adipose tissue. As oppose to inflammation triggered by a pathogen, chronic inflammation or metaflammation induced in the context of excess nutrient intake does not resolve and directly leads to a decrease of insulin sensitivity. As energy imbalance persists and metabolic syndrome progresses, not only the adipose tissue, but also the liver, the pancreas, and the muscles are sites of inflammation and insulin resistance (3). The role of key immune molecules, such as pathogen sensors like toll-like receptors (TLR) in metabolic syndrome and obesity has been demonstrated by showing that their ablation in mice conferred protection against insulin resistance (13). Thus, classical pathways of inflammation used to activate the immune system in the context of an infection are primed in the context of metaflammation. This leads us to speculate that these pathways might be altered and less prone to react in the event of an infection (3).

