To support our hypothesis, several studies have demonstrated that during the 2009 influenza H1N1 pandemic, obesity was associated with more severe infection and death (6, 14). The mechanism is likely immune mediated but has not been determined yet (15). Also, it has been reported that obese people might be less protected by influenza vaccination (7). The area of systems biology has considerably contributed to a better understanding of vaccine efficacy (10, 16). Gene expression studies using peripheral blood can predict vaccine response to influenza (10, 11). High vaccine response correlates with the expression of interferon signaling (genes like STAT1, IRF9) and antigen processing and presentation. To test our hypothesis, we contacted the authors of a study published in Cell in 2014 (12) and obtained the BMI of the patients. The study demonstrated the ability to predict the influenza vaccine response using several parameters. We focused on the immune response based on antibody titers and the gene expression profile at D0 and D1. We separated the individuals in 2 groups: one group of lean (BMI<25) and one group overweight and obese (BMI>25). The two groups contained 25 and 17 individuals respectively. We observed a trend towards an inverse correlation of the immune response to influenza vaccine with increasing BMI. Also, we analyzed the differential gene expression profile between D0 and D1 between the two groups. JUN Kinase, Stat1 and IRF1 were among the most up-regulated genes in the lean group but not in the overweight and obese group. When comparing the two groups using ingenuity pathway analysis, the role of PKR in interferon response, Toll like receptor signaling, Natural killer cell signaling were more activated in the lean group compare to the overweight and obese group. These results indicated that the innate immune response induced by the vaccine might be attenuated in the overweight and obese group. BMI was the only factor used for this analysis and we did not have access to any metabolic marker. Obesity is not necessarily associated with an unhealthy metabolic status. Therefore, we would now like to focus on metabolic syndrome as it better correlate with an unhealthy metabolic status. Our aim is to determine if metabolic syndrome attenuates the immune protection induced by the vaccine and establish the molecular mechanism of antiviral immune deficiency associated with metabolic syndrome. We would like to know if differences between people with and without metabolic syndrome can be seen at the molecular level and correlate with differences in antibody titers. We believe our study will contribute to 1/ better understand vaccine efficacy 2/ establish if the low-grade chronic inflammation associated with metabolic syndrome impacts the systemic immunity against viral infection.

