**SCREENING VISIT #1**

Consent

Medical history

Physical examination including height and weight to determine BMI, and waist circumference

Vital Signs - If the initial blood pressure is above 150/90 mmHg upon arrival to the OPRC, a second B/P will be taken by the LIP during the screening process. The average of the two readings will be the enrollment criterion.

POCT - HIV

POCT - urine pregnancy test

Labs: HbA1c - (1) 3.0 ml lavender tube

Hepatitis Panel - (1) 8.5ml SST marble top tube

Comprehensive metabolic & CRP - (1) 8.5 ml SST marble top tube

CBC - 3 ml lavender top tube

Gene expression - (3) 2.5ml Pax RNA tube (total 7.5ml).

Influenza A & B antibodies - (1) 10ml red top tube

Total blood volume to be drawn for screening visit 1 = 40.5ml .

Instructions to return fasting for 8 hours prior to the next visit.

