**Statistical Analysis**

To compare the means of antibody titers between groups (healthy volunteers and metabolic syndrome participants) a t-test at 95% significance level will be performed if the data follows a normal distribution, otherwise a non parametric Wilcoxon-Mann-Whitney test will be used.

A Chi-square test at 95% significance level will be used for the comparison of percentage of participants achieving a determined level for the HI antibody titer and rates of seroconversion. On that case if any observed frequency is smaller than 5 Fisher exact test will be used instead of Chi-square.

Expression values will be modeled using mixed-effect models, with group as fixed factor, and a random effect for each participant. FCHs for the comparisons will be estimated, and hypothesis testing conducted.

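### The gene-expression model has no visit or group-by-visit term, so one group coefficient per gene mixes pre-vaccine differences with differences in vaccine response

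*Combined protocol and SAP*

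**What the plan says.** The expression model is in the Statistical Analysis text that follows Section 11.9: "Expression values will be modeled using mixed-effect models, with group as fixed factor, and a random effect for each participant". The next sentence is "FCHs for the comparisons will be estimated, and hypothesis testing conducted". The comparisons are not named, and the plan does not say which samples enter the model. Section 11.8 adds only who will help run the RNA-seq analysis.

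Section 11.7 schedules expression samples at six visits: Screening 1 ("Gene expression - (3) 2.5ml Pax RNA tube (total 7.5ml"), Day 0 before the vaccine, and Days 1, 7, 28 and 90.

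The scientific interest is described in three places:

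- Section 7.1 hypothesizes that "differences in the innate immune responses between individual with or without metabolic syndrome impact viral infection and vaccine outcome".
- Section 11.1 describes the investigators' reanalysis of another data set, where the Day 0 to Day 1 expression change was compared between BMI groups. They conclude that "the innate immune response induced by the vaccine might be attenuated in the overweight and obese group".
- Section 11.1 also states a broader aim: "We would like to know if differences between people with and without metabolic syndrome can be seen at the molecular level".

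Section 11.6 lists the expression profile as one of three secondary outcomes, without ranking them.

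**The concern.** Two different quantities are of interest for each gene. One is a constitutive difference between the groups, present before vaccination. The other is a difference in how expression changes after vaccination. The second is a group-by-visit contrast, and a model with group as its fixed factor has no parameter for it.

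The rationale makes both plausible. Section 11.1 says that "classical pathways of inflammation used to activate the immune system in the context of an infection are primed in the context of metaflammation", and speculates that "these pathways might be altered and less prone to react in the event of an infection". If, for some gene, the first raises expression in metabolic syndrome and the second lowers the response, the two enter the single coefficient with opposite signs.

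A significant coefficient could then not be attributed to baseline inflammation or to vaccine response, and a null coefficient could hide both. Because the comparisons are unnamed, the contrast could also be chosen after the data are seen.

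**Working it through.** The plan gives no power, effect size or variance for expression, so there is no figure of its own to reproduce.

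**Step 1: what the coefficient estimates.** The stated model is y = a + b·group + u(participant) + e. With complete data, the estimate of b is the mean of the visit-specific group differences:

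b = (d_S1 + d_D0 + d_D1 + d_D7 + d_D28 + d_D90)/6

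Two of the six terms are pre-vaccine. If a constant offset d is present at all visits and a response difference r at k of them, then b = d + k·r/6. This needs no assumption about effect size.

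- Day 1 difference of 1 SD only (d = 0, r = 1, k = 1): b = 1/6.
- Constant offset of 1/6 SD and no response difference (d = 1/6, r = 0): b = 1/6. The two cases cannot be told apart.
- Offset +0.5 SD with a response 0.75 SD lower at all four post-vaccine visits: b = 0.5 − 0.75 × 4/6 = 0.

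**Step 2: illustrative power.** The group size of 20 is from Section 11.9. Assumed, because the documents give no values: total SD 1; between-person variance τ² and within-person variance σ² with τ² + σ² = 1; two-sided 5% per gene; noncentral t with 38 df. Standard errors:

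- Group-only, six visits: √[(2/20)(τ² + σ²/6)]
- Group-only, Days 0 and 1: √[(2/20)(τ² + σ²/2)]
- Day 1 minus Day 0 between groups: √[(2/20)(2σ²)]
- Mean of four post-vaccine visits minus Day 0: √[(2/20)(1.25σ²)]

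Power for a 1 SD response difference and no offset:

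| Analysis | σ² = 0.7 | σ² = 0.5 | σ² = 0.3 |
|---|---|---|---|
| Group-only, Day 1 only (b = 1/6) | 0.125 | 0.103 | 0.091 |
| Group-only, Days 1 and 7 (b = 2/6) | 0.357 | 0.270 | 0.220 |
| Group-only, Days 1, 7 and 28 (b = 3/6) | 0.665 | 0.523 | 0.429 |
| Group-only, all four post-vaccine visits (b = 4/6) | 0.889 | 0.767 | 0.660 |
| Group-only, only Days 0 and 1 modelled (b = 0.5) | 0.481 | 0.429 | 0.387 |
| Day 1 minus Day 0 contrast | 0.740 | 0.869 | 0.978 |
| Same contrast, per-gene 0.001 | 0.210 | 0.363 | 0.692 |
| Mean post-vaccine minus Day 0 (difference at all four) | 0.909 | 0.974 | 0.999 |

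In the cancelling case, group-only power is 0.050 throughout, and the Day 1 minus Day 0 contrast (−0.75 SD) has 0.498, 0.637 and 0.847.

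**Step 3: simulation checks.** In the cancelling case, 20,000 simulated data sets per setting gave group-only rejection of 0.051, 0.047 and 0.052, and contrast rejection of 0.498, 0.639 and 0.844. Mixed models fitted to 150 data sets each at σ² = 0.7 and 0.3 (a few with convergence warnings) gave mean group-only coefficients of −0.016 and 0.006. The group-by-visit model recovered Day 1 minus Day 0 differences of −0.745 and −0.752, and Day 0 differences of 0.477 and 0.499.

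Under other assumed values (between-person and residual SD both 0.5), a constant difference of 0.2 gave a group-only coefficient of 0.207, and a Day 1-only difference of 1.2 gave 0.213. The Day 1 minus Day 0 contrast separated them: 0.00 and 1.22.

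**The case against.** The model is described in two sentences of an application form. The text does not say that group is the only fixed factor, and the plural in "FCHs for the comparisons will be estimated, and hypothesis testing conducted" suggests contrasts that were not written down. On that view the plan is merely under-specified. This stands in part: the intended analysis may be richer. But a group-only model cannot yield visit contrasts, so if they are intended the model sentence needs the same correction. Separate fits per visit do not fit the text either: with one value per participant at a visit, a participant random effect cannot be told apart from residual error.

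The exact-zero case is chosen to cancel, and Section 11.1 speculates about a weaker response without giving a direction for any gene's baseline level. This stands. With the same sizes but the deficit on Day 1 only, b = 0.5 − 0.75/6 = 0.375 and group-only power is about 27-43%; with Days 1 and 7, b = 0.25 and power is 14-22%. The misattribution remains in both.

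The power values rest on assumed inputs and a large effect. This also stands. For a 0.5 SD difference the Day 1 minus Day 0 contrast has only about 26-51% at 5% and 2-8% at 0.001. The algebra in Step 1 carries the point.

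Finally, the group term does partly answer whether the groups differ at the molecular level.

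**Conclusion.** The concern holds. As written, the model estimates one visit-averaged group difference per gene and has no term for a group difference in post-vaccine change. A difference on one of six visits is diluted to a sixth of its size, and constitutive and response effects cannot be separated.

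The averaging follows from the model. It is an equal-weight mean with complete visits; with missing visits it is a weighted mean that still mixes pre- and post-vaccine differences. The size of the power loss depends on the assumed variances and on how long a response difference lasts, from severe (Day 1 only) to modest or none (all post-vaccine visits).

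The change should be made, but its reach is limited: expression is a secondary outcome and the primary antibody comparison is unaffected.

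**What to change.** In the Statistical Analysis text:

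1. State which samples enter the expression model.
2. Fit group, visit (categorical) and group-by-visit fixed effects with a participant random effect, with Day 0 as the pre-vaccine reference.
3. Name the between-group difference in Day 1 minus Day 0 change as the key expression contrast, with later visits secondary.
4. Report the Day 0 group difference separately as the constitutive difference.
5. Do not pool Screening 1 into baseline by default; keep it for a sensitivity analysis at most. The visit windows in Section 11.7 allow up to about 14 + 30 + 7 = 51 days between Screening 1 and Day 0. Criterion 14 in Section 12.12 also appears to except the screening visits from the infection criterion, although its wording on rescheduling is ambiguous.

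The cost is a few lines of text and two model terms; no new data are needed. There is one trade-off. If a difference persists through all post-vaccine visits and σ² is 0.7, the Day 1 minus Day 0 contrast has less power than the group-only coefficient (74% against 89%). The mean post-vaccine minus Day 0 contrast from the same model has 91% and can be listed as a secondary contrast. The change does not by itself secure adequate power at a genome-wide threshold, as the 0.001 row shows.

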**11.8 \* Data Analysis**

Describe method(s) of data analysis. Include the role of external collaborators as appropriate.

As per recommended by the food and drug administration (17), the hemagglutination inhibition (HI) antibody assay has been used to assess vaccine activity and may be appropriate for the evaluation of the pandemic influenza vaccine. Appropriate endpoints may include: 1) the percentage of subjects achieving an HI antibody titer  $\geq 1:40$ , and 2) rates of seroconversion, defined as the percentage of subjects with either a pre-vaccination HI titer  $< 1:10$  and a post vaccination HI titer  $> 1:40$  or a pre-vaccination HI titer  $\geq 1:10$  and a minimum four-fold rise in post-vaccination HI antibody titer. Previous study have built models using both HAI and neutralization assays to determine vaccine responsiveness.

The RNA-seq analysis will be run with the help of the Genome resource center as well as the expertise of [name] listed as a collaborator of this project.

**11.9 \* Explain the rationale for the choice of statistical measures and the number of subjects proposed for the study, including the power calculations when applicable.**

Since no preliminary data is available to estimate the percentage of participants achieving a determined level for the HI antibody titer and the rate of seroconversion for each group (healthy volunteers and metabolic syndrome participants) we provide an estimation of the minimum effect size for the sample size selected is able to detect. For a sample size of 40 participants, 20 at each group, a 95% significant Chi-square test will be able to detect an effect size equal or larger than 0.56 with 0.8 power. It means that a Chi-square test will be able to detect independence between groups if the distance between the observed odd ratio is larger than 1.56.

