## 16.0 Recruitment and Advertising

**For assistance consult CRSO to create a robust Recruitment Plan see Help.**

### 16.1 \* What is the plan for recruitment?

**Overview:**

The CRROSS will prescreen up to 100 volunteers in order to enroll 20 with a metabolic syndrome and 20 healthy controls to achieve the goal of 40 evaluable participants at study completion. Healthy controls will be age matched (+/-5 years) and gender matched to the metabolic syndrome participants.

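### The RNA-seq analysis fixes no error rate, contrast or gene set, although the plan's own Day 0 to Day 1 candidates would support one pre-specified test

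*Combined protocol and SAP*

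**What the plan says.** The Statistical Analysis text under 11.9 gives expression two sentences. The first sets up a mixed-effect model with group as the fixed factor and a random effect for each participant. The second is "FCHs for the comparisons will be estimated, and hypothesis testing conducted". No level, false-discovery or familywise procedure, gene filter, gene list or list of comparisons follows. The 5% level (worded as 95%) is attached to other tests: the titer means, where "a t-test at 95% significance level will be performed if the data follows a normal distribution", and the responder rates, where "A Chi-square test at 95% significance level will be used for the comparison of percentage of participants achieving a determined level". Sections 11.7 and 11.8 add only that a genomics core and a collaborator will help with RNA-seq.

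Section 11.1 is more specific about what is expected. From earlier literature: "High vaccine response correlates with the expression of interferon signaling (genes like STAT1, IRF9) and antigen processing and presentation". From the investigators' own reanalysis of a published cohort (25 lean, 17 overweight or obese; Day 0 against Day 1): "JUN Kinase, Stat1 and IRF1 were among the most up-regulated genes in the lean group", but not in the heavier group. The PKR/interferon, Toll-like receptor and natural killer pathways were also more activated in the lean group.

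Section 11.6 lists the expression profile as a secondary outcome. Section 11.7 schedules RNA samples at the first screening visit and on Days 0, 1, 7, 28 and 90.

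**The concern.** Expression carries the mechanistic aim: whether the early innate response is blunted in metabolic syndrome and whether that tracks antibody response. As written, the genes, time points and threshold that define a finding can all be chosen after the results are seen. An unadjusted gene list could contain hundreds of chance findings. A corrected genome-wide search with 20 per group loses much of its power for moderate effects.

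The model adds a second difficulty. Taken literally, with group as the only fixed factor, the group coefficient compares expression levels averaged over each person's samples, not the change after vaccination. If all six sampling times entered and the groups differed only on Day 1, by an amount D, the averaged contrast would be D/6. The question raised in 11.1 is about the Day 0 to Day 1 change.

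**Working it through.** **Inputs from the documents.** Size and allocation: "For a sample size of 40 participants, 20 at each group" (11.9). Section 16.1 recruits "to achieve the goal of 40 evaluable participants at study completion", so no further loss is deducted.

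**Assumptions, because the plan gives no figure.** Genes tested: 5,000 to 20,000, with 15,000 as the central case. Level if unadjusted: 5%, two-sided. Share of genes truly different: 1% to 20%. Standardised difference d, on the scale of the between-person SD of the quantity tested: 0.91, with 0.5 as a smaller case. Genes are treated as independent; correlation leaves expected counts unchanged but makes them more variable.

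**The plan's own figure.** The only power statement, "will be able to detect an effect size equal or larger than 0.56 with 0.8 power", concerns the chi-square test of antibody responders. It does not reproduce: with N = 40, 1 degree of freedom and 5%, the detectable effect is (1.960 + 0.842)/√40 = 0.443. That is a separate matter and is not used here. No figure is given for expression.

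**1. False genes at an unadjusted 5% if none differs.** Expected number = genes × 0.05: 5,000 gives 250, 10,000 gives 500, 15,000 gives 750, 20,000 gives 1,000.

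**2. One between-group test, 20 v 20.** Two-sample t, 38 degrees of freedom, noncentrality d × √(20/2). At d = 0.91 this is 0.91 × 3.162 = 2.88.

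| Level | d detectable at 80% power | Power at d = 0.91 |
|---|---|---|
| 0.05 (one pre-specified test) | 0.91 | 80% |
| 0.0005 | 1.49 | 20% |
| 0.05/15,000 = 3.3 × 10⁻⁶ (Bonferroni) | 2.02 | 1.6% |

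At d = 0.5 the single test at 5% has 34% power.

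**3. Benjamini-Hochberg at 5% over 15,000 genes, d = 0.91.** With share p truly different, the p-value cut t is the largest value satisfying t / [(1 − p)t + p × power(t)] ≤ 0.05. The last column is the false share of an unadjusted 5% list: 15,000(1 − p)(0.05) false genes against 15,000p(0.80) true ones.

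| Share truly different | BH cut | Average power per gene | False share of an unadjusted 5% list |
|---|---|---|---|
| 1% | 0.000026 | 5% | 742.5/(742.5 + 120) = 86% |
| 5% | 0.00056 | 21% | 712.5/(712.5 + 600) = 54% |
| 10% | 0.0017 | 33% | 675/(675 + 1,200) = 36% |
| 20% | 0.0048 | 46% | 600/(600 + 2,400) = 20% |

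A simulation of 15,000 independent genes agreed with the power column to within a percentage point.

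**4. Larger effects.** In the same kind of simulation, Benjamini-Hochberg power at d = 1.0 is 35% to 61% when 5% to 20% of genes differ. At d = 1.5 it is at least 79% across the 1% to 20% range.

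**The case against.** Several objections have force.

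- **Analysts would apply a false discovery rate anyway.** Probably so. Stating one is routine detail that the core or the collaborator would supply. What they would not supply unprompted is the single contrast and gene list fixed in advance, and that is where the gain lies.
- **A reader might infer that the plan tests each gene at 5%.** The text does not say so: that level belongs to the titer and responder tests. The 250 to 1,000 false genes are conditional on that reading.
- **A reader might infer that an unadjusted list would be mostly false.** That needs about 5% or fewer of the genes to differ. The documents give no such share.
- **A reader might infer that correction leaves almost no power.** That holds for Bonferroni at moderate effects and for false-discovery control when few genes differ. It is not general, as step 4 shows.
- **Comparing a score with a gene at the same d is an assumption.** A score's d depends on how many of its genes respond and how they correlate, and the documents give neither. A score may do better or worse than 0.91.
- **The candidates come from a different contrast.** The reanalysis split people at BMI 25, and 11.1 says no metabolic marker was available. IRF9 comes from the cited literature, not from that reanalysis. This limits confidence in the candidates, but a wrong candidate costs one negative test and leaves the exploratory search intact.
- **Time effects may be intended.** The plural in the expression sentence and the participant random effect suggest repeated measures. No time term or time contrast is written down.

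**Conclusion.** The point holds as a gap in a secondary analysis. The expression plan leaves error rate, contrast and gene set open, and does not use directional candidates that the plan itself reports. The 250 to 1,000 false genes rest on 5,000 to 20,000 genes at an unadjusted 5% with no true differences. The power comparison (5% to 46% per gene under false-discovery control, against 80% for one test) rests on 15,000 genes, 1% to 20% truly different, and d = 0.91 for both gene and score. At d = 0.5 even the single test has only 34% power, so pre-specification improves the chance of an answer without guaranteeing one. A reader might also infer that the trial's main conclusion is at risk. The documents do not support that: the primary outcome is antibody response, with its own tests.

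**What to change.** Replace the two expression sentences with text to this effect:

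> The key expression comparison is the between-group difference in the Day 1 minus Day 0 change of one interferon-response score, defined as the mean log2 expression of a listed gene set (for example STAT1, IRF1, IRF9 and named interferon/PKR pathway genes). It is estimated from a mixed model with group, time and group-by-time terms and a random participant effect, and tested at two-sided 5%. The gene list is fixed and dated before any expression data are analysed by group. All other genes, pathways and time points are exploratory, reported at a Benjamini-Hochberg false discovery rate of 5% across genes and the listed contrasts.

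The dating rule is tied to analysis by group because the documents describe no unblinding step and the sample codes in 11.10 carry the cohort letter.

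If a single score is not wanted, a short gene list with familywise control is a workable alternative. Four named genes at 0.05/4 = 0.0125 each have a detectable d of 1.10, against 0.91 for one test.

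The cost is wording and a gene list; no extra participants, samples or visits are needed. The downsides are that fewer single genes can be called significant, and that the score rests on candidates from a BMI contrast rather than a metabolic syndrome contrast. The report should state that limitation.
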